## 5. Study Objectives and Endpoints

### 5.1. Primary Objectives

- To evaluate the pharmacokinetics of dolutegravir (DTG) during the first 28 days of life in HIV-exposed term neonates (born to a mother with HIV) following administration of DTG dispersible tablet
- To determine the safety of DTG during the first 28 days of life in HIV-exposed term neonates following administration of DTG dispersible tablet

### 5.2. Secondary Objectives

- To assess the acceptability of DTG dispersible tablet for the neonate and the caregiver

### 5.3. Endpoints

#### 5.3.1. Primary endpoints

- DTG plasma pharmacokinetics parameters: area under the concentration time curve (AUC); maximum plasma concentration ( $C_{max}$ ), apparent clearance (CL/F), and trough concentration ( $C_{trough}$ )
- Occurrence of the following events: adverse events of Grade 3 or higher; treatment-related adverse events of Grade 3 or higher; any adverse events

#### 5.3.2. Secondary endpoints

- Acceptability to caregivers and neonates of using DTG-DT will be measured by means of a questionnaire

## 6. Study Design and Setting

### 6.1. Study Design

A Phase I/II, open-label, single arm, two-stage trial to evaluate the single and multi-dose PK and safety of DTG in HIV-exposed neonates on ARV prophylaxis. HIV-exposed term neonates born mothers with HIV on DTG-based antiretroviral therapy with a birth weight  $\geq 2000$  g who are on ARV postnatal prophylaxis will be enrolled.

Subject will be enrolled in two stages:

- **Stage 1** will assess a single 5 mg dose of the DTG dispersible tablet in two sequential cohorts: Cohort 1A (n=8) and Cohort 1B (n=8).
- **Stage 2** will assess multiple 5 mg doses of the DTG dispersible tablet in a single cohort: Cohort 2 (n=24).

Per national guidelines, all infants receive a birth HIV nucleic acid test (NAT). HIV NAT test results for the infant may or may not be available (HIV pending) at the time of study entry. HIV NAT results are typically available within 72 hours of the blood sample being taken and are checked and acted upon by the hospital HIV PMTCT service, as part of standard of care (Section 9.1). If an HIV NAT result comes back positive whilst the neonate is on study, the neonate will not receive any further DTG doses, revert to standard of care antiretroviral therapy (ART), and be followed for safety for the duration of the study.

### 6.1.1. Stage 1: Single Dose of the DTG generic dispersible tablet

Cohort 1A will open to accrual first (Schema, Section 6.2, **Figure 1**).

- **Cohort 1A:** 8 neonates weighing  $\geq 2000$  g at birth will receive a single dose of 5 mg DTG at  $\geq 14$  days and  $< 28$  days of life.

DTG will be administered in addition to standard of care ARV prophylaxis. After Cohort 1A is complete, and if no safety concerns are noted, accrual will continue into Cohort 1B. However, if safety hold criteria are met in Cohort 1A (Section 11.1.1), the study will be paused and data reviewed by the DSMB.

- **Cohort 1B:** 8 neonates weighing  $\geq 2000$  g at birth will receive a single dose of 5 mg of DTG at  $< 14$  days of life.

If safety hold criteria are met during Cohort 1B (Section 11.1.2), the study will be paused and data reviewed by the DSMB. After Cohort 1B is complete, all safety and PK data for **Stage 1** will be reviewed. Pharmacokinetic modelling and simulation analyses using Stage 1 PK data will be performed to select the multi-dose schedule of the DTG dispersible tablet for Cohort 2 (Section 11.4). All findings will be presented to the DSMB and agreed upon before opening Cohort 2.

[figure not shown]
### 6.1.2. Stage 2: Multi-Doses of the DTG generic dispersible tablet

- **Cohort 2:** 24 neonates weighing  $\geq 2000$  g at birth will receive multiple 5 mg doses of DTG starting within 7 days of life until day 28.

Low-risk\* term neonates born to virologically suppressed mothers enrolled in Stage 2 will receive ZDV prophylaxis, instead of NVP, for the duration of the study. An interim PK and safety analysis will be performed after 50% of participants have completed Cohort 2 to assess if a dose adjustment is required and to review safety data. If no major safety or PK concerns are noted, enrolment into Cohort 2 will continue. If needed, a different DTG dosing schedule may be selected based on the data available for the remainder of Cohort 2 infants. Any change to the DTG dosing schedule will be agreed upon by the DSMB before implementation.

*[\*Low risk: Neonate born to a mother with a plasma HIV-1 RNA result  $< 50$  copies/mL in the 4 weeks prior to delivery or between delivery and infant study entry]*

## 6.2. Study Schema

**Figure 1: PETITE-DTG Study Schema**

## 6.3. Study Setting

This single site study will be implemented at the Family Centre for Research with Ubuntu (FAMCRU), an academic research centre in the Department of Paediatrics and Child Health, Faculty of Medicine and Health Sciences (FMHS), Stellenbosch University (SU). FAMCRU is located within the associated Tygerberg Hospital (TBH), a large secondary and tertiary referral centre situated in the Western Cape Province, South Africa.

In South Africa, 7,800,000 people were living with HIV in 2020, with an HIV prevalence among adults (15-49 years) of 19.1%. Newly infected people with HIV were 230,000, and 83,000 people died from an AIDS-related illness. Women are disproportionately affected by HIV in South Africa. Of the 7,800,000 adults living with HIV, 4,800,000 (61.5%) were women. New HIV infections among young women aged 15 to 24 years were more than double those among young men: 140,000 new infections among young women, compared to 77,000 among young

men. ARVs to prevent vertical HIV transmission was accessed by 97 (60->98) % of pregnant women living with HIV, preventing 52,000 new HIV infections among newborns (23).

The national maternal HIV prevalence in South Africa remains high at around 30 %, but vertical transmission rates in the first 2 months of life have decreased to 0.7% in 2019, with the remainder of childhood transmissions occurring during the breastfeeding period (24). Prevention of mother-to-child transmission (PMTCT) services are well established, with all pregnant women qualifying for combination ART. In June 2021, the South African National Department of Health released a circular (Reference: 2021/06/29/EDP/01) updating guidance for the use of DTG in pregnancy, now supporting the use of a DTG preferred first-line ART regimen for all adults living with HIV, including pregnant women and women of child-bearing age (25). A statement from the South African Clinicians' Society followed soon afterwards recommending that all women, including pregnant women, preferentially be started on tenofovir/lamivudine/dolutegravir (TLD) (26), which has been the clinical practice since.

In South Africa, women with HIV routinely receive an HIV-1 RNA viral load (VL) at delivery and their infants receive a minimum of 6 weeks of ARV postnatal prophylaxis, dependent on the risk of HIV acquisition in the infant. HIV-exposed neonates start a prophylaxis regimen of nevirapine (NVP) and zidovudine (ZDV) at birth and continue this until the maternal VL result at delivery is available. If the maternal VL is  $\geq 1000$  copies/mL the infant is classified as 'high-risk' and continues both ARVs, else infants are deemed 'low'-risk and ZDV is stopped and NVP continued. All HIV-exposed neonates receive an HIV NAT test at birth, 10 weeks, 6 months, and in those who are breastfed, at 4 weeks post-cessation of breastfeeding (1).

## 7. Selection of Participants

All relevant medical and non-medical conditions must be taken into consideration when deciding whether this protocol is suitable for a participant. Any questions regarding a participant's eligibility should be discussed with the Principal Investigator (PI) prior to the participant's enrolment.

Prior to screening and enrolment for the study the parent(s) or legal guardian must give written consent for the neonate to participate in the study.

### 7.1. Inclusion Criteria

Written informed consent to participate in the study must be obtained for all participants from the parent(s) or legal guardian.

#### Stage 1: Inclusion Criteria

- HIV-exposed neonate (pending HIV status) born to a woman with HIV on DTG-based ART
- Birth weight of  $\geq 2000$  g and on standard of care ARV prophylaxis

Cohort Specific Inclusion Criteria in Stage 1 must be met at **Study Entry:**

**Cohort 1A:** Infant <14 days of life

**Cohort 1B:** Infant  $\leq 3$  days of life

## Stage 2: Inclusion Criteria

- Low risk\* HIV-exposed neonate (pending HIV status) born to a virologically suppressed woman on DTG-based ART
  - *\*Neonate born to a woman with a documented plasma HIV-1 RNA result <50 copies/mL in the 4 weeks prior to delivery or between delivery and infant study entry*
- Birth weight of  $\geq 2000$  g and on standard of care ARV prophylaxis

Cohort Specific Inclusion Criteria in Stage 2 must be met at **Study Entry**:

**Cohort 2:** Infant <7 days of life

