### 9.2.2.2. Cohort 1B: Safety Visits

One week after PK Visit 1a (+/-4 days), we will conduct a clinical and laboratory safety visit. Medical staff will take a recent medical history from the parent(s) and examine the neonate. Study required bloods will be drawn, and an HIV NAT will be performed. If any tests yield abnormal results, as specified by protocol specific safety criteria (Section 10), we will consult with paediatricians for appropriate management of the neonate. If all tests are normal, a telephonic safety visit will be conducted 2 weeks after PK Visit 1a (+/-4 days). Medical staff will once again take a recent medical history from the parent(s). If no issues are reported, the neonate will exit the study at the conclusion of this visit. If any concerns are noted, the neonate will be brought back for clinical and special investigations as needed. The total study duration for each individual will depend on the age at enrolment and can range from 3 to 4 weeks.

If study safety hold criteria (Section 11.1.2) are met at any time during Cohort 1B the study will be paused, safety data reviewed, and a DSMB meeting held to determine if the study should continue (Section 6.2, **Figure 1**). After Cohort 1B is complete, all safety and PK data for Stage 1 will be reviewed. Pharmacokinetic modelling and simulation analyses using Stage 1 PK data will be performed to select the multi-dose schedule of 5 mg DTG for Cohort 2. All findings will be presented to the DSMB before opening Cohort 2 (Section 11.4).

### 9.2.3. Stage 2: Cohort 2

Low-risk HIV-exposed neonates in Cohort 2 will receive multiple 5 mg doses of DTG.

DTG administration will begin within 7 days of life and continue until day 28 of life on top of ARV postnatal prophylaxis. Due to the potential drug-drug interaction between NVP and DTG, the low-risk neonates enrolled in Stage 2 will receive ZDV prophylaxis, instead of NVP, for the duration of the study (Section 8.2.1 and Section 13.6).

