### 9.2.3.1. Cohort 2: Screening and Entry visit(s)

The screening and entry visit(s) will take place when the neonate is <7 days of life (Section 9.1). Screening and entry procedures may be performed as one or 2 separate visit(s). At the Entry visit, ZDV prophylaxis will be initiated instead of NVP and continue until DTG is stopped at Day 28 of life. Thereafter, the infant will switch back to NVP from ZDV and continue prophylaxis per national guidelines.

The study team will support the preparation and administration of the 1st dose of the DTG-DT (half-tablet) mixed with water with the parent(s) or caregiver/legal guardian. The exact time of intake will be recorded. The mother will be explained how to prepare and administer DTG at home. Acceptability testing of the DTG-DT will be performed.

Two blood samples will be drawn for PK assessment, one sample immediately prior to administering the 1st DTG dose and another sample at 1-3 hrs post-dose (**Table 5**). It is planned to draw 0.4 mL of blood per time point.

### 9.2.3.2. Cohort 2: Study Visits 2 and Visit 3

It is anticipated that DTG could be dosed every 24, every 48 or every 72 hours, or some other combination, that is expected to achieve target DTG concentrations throughout the first 4 weeks of life. The PK sampling schedule has been designed to cover these different possible dosing scenarios.

After the Entry, Visit 2 can be scheduled at **any time from the 3rd dose of DTG** but before Week 4 of life. The mother will be instructed not to administer the morning DTG dose prior to attending this study visit. On the morning of Visit 2, clinic study nurses and physicians will take a medical history, examine the neonate, and assess adherence. Assessments will include dispensing diary cards to caregivers, reviewing or collecting diary cards and establishing study drug adherence (pill count). The PK assessment should be deferred if the mother/caregiver reports their baby missing any of the previous 3 scheduled doses prior to the PK sampling visit (Section 9.4).

Prior to the morning DTG dose, a blood sample will be taken for pre-dose PK evaluation and then the protocol-specified DTG dose will be administered. The exact time of intake will be recorded. Acceptability testing of the DTG-DT will be performed.

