#### 9.2.3.4. Cohort 2: Visit 5 and Safety Phone call

Study Visit 5 will be performed in Week 4 of life (Day 22 to 28 of life). The mother will be instructed not to administer the morning DTG dose prior to attending this study visit. Medical staff will take a recent medical history from the parent(s) perform a clinical and laboratory safety visit. Adherence assessment and acceptability testing of DTG will be performed. Study required bloods will be drawn at visit 5, including an HIV NAT test. If any tests yield abnormal results, as specified by protocol specific safety criteria (Section 10), we will consult with paediatricians for appropriate management of the neonate.

Two blood samples will be drawn for PK assessment, one sample immediately prior to administering the morning DTG dose and another sample at 1-3 hrs post-dose (**Table 5**). It is planned to draw 0.4 mL of blood per time point.

The administration of DTG will be stopped by day 28 of life, after which local ARV prophylaxis will be continued as per standard of care.

A telephonic safety visit will be conducted 2 weeks after Visit 5 (+/-4 days). Medical staff will once again take a recent medical history from the parent(s). If no issues are reported, the neonate will exit the study at the conclusion of this visit. If any concerns are noted,

the neonate will be brought back for clinical and special investigations as needed. The total study duration for each individual will depend on the age at enrolment and can range from 5 to 6 weeks.

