## 10.8. Participant Study Drug Discontinuation Criteria

For all AEs/toxicity, the management and temporary/permanent discontinuation of the study drug should generally follow the criteria below, but clinicians should use their clinical judgment as to the best management for an individual participant.

- Grade 1 and Grade 2 AEs/toxicity:  
Continue the study drug. Manage using symptomatic measures and other concomitant medication, if appropriate.
- Grade 3 AEs/toxicity:  
Request laboratory results and repeat confirmatory laboratory results within 72 hours if relevant. Continue study drug pending receipt of the confirmatory laboratory tests/repeat observations, unless there is an immediate need to substitute ART. Continue to work-up to exclude other causes. Following confirmation of toxicity, and lack of other cause data (i.e., possibly, probably, or definitely related to the study drug) hold the treatment and follow abnormal laboratory values until they are Grade 2 or less.
- Grade 4 Potentially Life-Threatening or Fatal AEs/toxicity:  
Request laboratory results and repeat confirmatory laboratory results within 72 hours if relevant. Withhold the study drug at the discretion of the site investigator/ health care provider for clinical events, while awaiting a repeat assessment/ confirmation of an abnormal laboratory test. Continue to investigate to exclude other causes and make an assessment on relation to study drug or not. Following confirmation of toxicity and lack of other cause data: (i.e., possibly, probably, or definitely related to the study drug) the study drug should be discontinued immediately. Participants who permanently discontinue study treatment due to an adverse event related to the study treatment will continue to be followed in the study for safety monitoring at intervals to be determined by the investigator in consultation with the study team.

Study drug will be **permanently discontinued in participants** with the following condition:

- any grade 4 event on the DAIDS toxicity table
- a bilirubin at exchange value

In addition, study drugs will not be administered to any participant if the HIV NAT result comes back as positive at any time during the study.

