### **13.6. Potential Benefits and Risks of the Research to the Subject**

The generic DTG 10 mg scored dispersible tablet from Viartis Ltd has received tentative approval from the U.S. FDA for use in infants and children 4 weeks and older and weighing at least 3 kg, and is currently under review with SAHPRA for regulatory approval in South Africa. Regulatory approval has not been requested for neonates due to lack of PK and safety data in this population. The PETITE-DTG study will generate this data for DTG in neonates, which will inform future ARV dosing and DTG use in neonates for HIV prevention and treatment.

We are proposing a study that requires the collection of personal and clinical data, as well as blood specimens, from neonates born to mothers living with HIV. Data will be entered into the clinical trial database by the site or CRFs may be scanned and emailed using secure encrypted systems to the data centre for data entry. All data will be de-identified and anonymised as to protect participant confidentiality. The PETITE-DTG study will comply with International General Data Protection Regulation (GDPR) and South African POPIA principles (Section 13.8). Most study procedures are routine medical procedures that are associated with minimal to no risk in participants. Blood collection may cause some discomfort and some bleeding or bruising may occur where the needle enters the skin. Well-trained and experienced study staff will perform the phlebotomy to minimize risk.

The potential risk of participation in this study is associated with the neonatal administration of DTG. Thus, all participants enrolled will be healthy HIV-exposed neonates born to mothers with HIV on a DTG-based ARV regimen. All neonates will be of term gestation and have a minimum birth weight of  $\geq 2000$  grams as no DTG data are available for preterm neonates.

In South Africa, women with HIV routinely receive an HIV-1 VL at delivery and their infants receives a minimum of 6 weeks of ARV postnatal prophylaxis, dependent on the risk of HIV acquisition in the infant. All HIV-exposed neonates start a prophylaxis regimen of NVP and ZDV at birth and continue this until the maternal VL result is available. If the maternal VL at delivery is  $\geq 1000$  copies/mL the infant is classified as 'high-risk' and continues both ARVs, else infants are deemed 'low'-risk and ZDV is stopped and NVP continued (1).

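### Stage 2 lets NVP be replaced by ZDV on an antenatal maternal viral load alone, with no rule for a delivery result that returns at ≥1000 copies/mL

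*Protocol*

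**What the plan says.** **Eligibility.** The Stage 2 criterion in protocol section 7.1 requires a "documented plasma HIV-1 RNA result <50 copies/mL in the 4 weeks prior to delivery or between delivery and infant study entry". The synopsis and sections 6.1.2 and 13.6 repeat the same either/or definition. Entry is before 7 days of life.

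**The switch.** Section 9.2.3.1 states: "At the Entry visit, ZDV prophylaxis will be initiated instead of NVP and continue until DTG is stopped at Day 28 of life". Section 9.2.3 says that "the low-risk neonates enrolled in Stage 2 will receive ZDV prophylaxis, instead of NVP, for the duration of the study". No exception is given in either place.

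**The national rule.** Section 6.3 explains that mothers have a routine viral load at delivery. Their infants start NVP and ZDV at birth "and continue this until the maternal VL result at delivery is available". Section 13.6 says the same: "All HIV-exposed neonates start a prophylaxis regimen of NVP and ZDV at birth and continue this until the maternal VL result is available". Under both sections, a result of ≥1000 copies/mL makes the infant high-risk and both drugs continue. Otherwise ZDV stops and NVP continues.

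**Late results.** Section 10.8 covers a late infant test: "study drugs will not be administered to any participant if the HIV NAT result comes back as positive at any time during the study". There is no matching text for a late maternal viral load.

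**The concern.** In standard care the delivery viral load decides whether an infant keeps both drugs. In Cohort 2 the study may withdraw one of them before that result is known, and the protocol does not say what follows if the result is unfavourable. Because the two windows are alternatives, an antenatal result below 50 copies/mL also satisfies the criterion literally when a higher delivery result is already on file.

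Section 13.6 justifies the change of prophylaxis by restricting Stage 2 to low-risk infants of suppressed mothers. It also says that the delivery result is not needed in Stage 1 because prophylaxis is unchanged there. In Stage 2 prophylaxis is changed, yet the delivery result is neither required nor followed up. An infant with a delivery result of ≥1000 copies/mL would be high-risk under the national rule while remaining, by study direction, off NVP.

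**Working it through.** There is no figure in the plan to reproduce. The check sets the provisions side by side, followed by two subtractions.

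**1. Can an infant enter without the delivery result?** Yes. The criterion in 7.1 is met by a result from the 4 weeks before delivery. The exclusion list in 7.2 does not mention maternal viral load. Section 9.1 has the study team take the qualifying result from the medical records and asks for nothing further.

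**2. Does anything later react to the delivery result?** I looked at:
- the Cohort 2 visit text (9.2.3.1 to 9.2.3.4) and Table 8: no step to obtain or review a maternal result;
- the drug discontinuation criteria (10.8): a positive infant HIV nucleic acid test (NAT), but no maternal result;
- the Cohort 2 hold criteria (11.1.3): related adverse events only;
- withdrawal (13.11): general investigator judgement;
- the PMTCT service (9.1): a general duty to see that mothers and infants receive suitable prophylaxis.

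None tells the study team to obtain the pending result or to reverse the switch.

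**3. How long would NVP be withheld if nobody intervened?** Inputs: entry on day 0 to 6 (before 7 days of life, 7.1) and ZDV in place of NVP until day 28 (9.2.3.1).

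Days without NVP = 28 − entry day
- Entry on day 6: 28 − 6 = 22 days
- Entry on day 0: 28 − 0 = 28 days

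The 28-day end is unlikely, because haematology and chemistry results must be available before entry (Table 8, note a).

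**4. Would the infant NAT fill the gap?** Not in time, and it answers a different question: it detects infection, not raised risk. After the screening/entry sample, Table 8 schedules the next NAT at Visit 5 (day 22 to 28). Section 9.2.3.4 confirms it: "Study required bloods will be drawn at visit 5, including an HIV NAT test".

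Interval from entry to the next NAT = Visit 5 day − entry day
- Shortest: 22 − 6 = 16 days
- Longest: 28 − 0 = 28 days

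**5. How often would the delivery result be pending at entry?** This cannot be calculated. The only turnaround given concerns the infant test (6.1): "HIV NAT results are typically available within 72 hours of the blood sample being taken". No maternal viral load turnaround is stated, and nothing gives the chance of moving from below 50 to ≥1000 copies/mL within 4 weeks.

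**The case against.** The strongest reply is that the eligibility window is deliberate. Section 13.6 notes that 50 copies/mL is stricter than the national 1000, and cites US guidance supporting 4 weeks of ZDV when suppression is shown within 4 weeks of delivery. That stands, and the window is not disputed here. As described in the protocol, though, that guidance does not deal with a delivery result that contradicts the earlier one.

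Second, there are safety nets. Arranging suitable prophylaxis is the PMTCT service's stated role, and 13.11 directs withdrawal when it is medically necessary. Either could lead to action. Neither names this case, and the drug change to be undone is one that the protocol itself ordered.

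Third, the event needs several things together: suppression within 4 weeks of delivery, ≥1000 copies/mL at delivery, the result pending or overlooked at entry, and inaction by both the service and the investigator, among 24 infants at one site. This stands, and is why no frequency is claimed.

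A reader might infer more than the text supports:
- **That these infants have no prophylaxis.** They receive ZDV and multi-dose DTG, and 13.6 says the combination may protect. The limit is that neonatal DTG dosing is what the trial is testing.
- **That the delivery result must be back before entry.** A review rule closes the gap without delaying enrolment.
- **That results of 50 to 999 copies/mL arriving after entry need their own step.** The national rule treats those infants as low-risk.
- **That the protocol should state how PK samples taken after an NVP restart are analysed.** That is ordinary content of the separate statistical analysis plan announced in 12.2.6.

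**Conclusion.** The point holds as a gap in the protocol's own instructions and should be fixed. Followed as written, the protocol can keep an infant who is high-risk under the national rule it describes on ZDV plus study DTG, without NVP, for about 22 to 28 days. That range is an upper bound: it assumes that neither the PMTCT service nor the investigator acts. Frequency is unknown and probably low. The reading of the text is firm; the size of any clinical consequence is not established by the documents.

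**What to change.** **Section 7.1 and its repeats (synopsis, 6.1.2, 13.6).** Base eligibility on the most recent maternal plasma HIV-1 RNA available at study entry, from within the two windows already stated, being below 50 copies/mL.

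**Sections 9.2.3.1 and 10.8.** Add: *If the maternal delivery viral load is pending at entry, the study team obtains and reviews it once available. If it is ≥1000 copies/mL, the infant returns to NVP plus ZDV under national guidelines, and the investigator decides whether DTG continues.* The DTG decision needs a named owner because 8.2.1 cites average adult falls of 19% in AUC0-24 and 34% in C24 with NVP.

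**Cost.** An amendment to wording. The test is already routine, and the entry window and the 13.6 rationale are unchanged. An occasional infant may lose evaluable PK data. Section 9.4 replaces only Cohort 2 infants who do not complete PK sampling at Visit 2, so one who completed that sampling would not be replaced as the text stands.
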